15. PUBLICATION POLICY

A detailed explanation of FibroGen's publication policy is described in the Clinical Trial Agreement.

APPENDIX A. SCHEDULE OF STUDY ASSESSMENTS

	Treatment Period ^a						Follow-Up Period ^b
	Baseline (Week 1)	Weekly Visits (Weeks 1-4) (± 3 days) ^c	Every 2 weeks (Weeks 6-24) (± 3 days)	Every 4 weeks (± 3 days)	Every 12 weeks (± 7 days)	Every 24 weeks (± 7 days)	Termination Visit or ET (± 3 days)
Written informed consent	X						
Eligibility criteria	X						
Dispense study drug	X	X	X	X	X	X	
Physical examination	X				X	X	X
Weight ^d	X ^e				X	X	X
BP, HR, respiratory rate	X	X	X	X	X	X	X
12-lead ECG	X ^e					X	X
hCG test for female subjects of child bearing potential only	X ^e						X
CBC with WBC differential and reticulocyte count	X	X	X	X	X	X	X
Fasting ^f serum chemistry (including LFTs, lipid panel, glucose)	X			X	X	X	X
Serum iron, ferritin, transferrin (or TIBC), TSAT	X			X	X	X	X
Special labs (CHr, hepcidin, hs-CRP, plus exploratory biomarkers) ^g	X ^e					X	X
Dose adjustment review			X	X	X	X	
Quality-of-life questionnaire (FACT-An)	X ^e					X	X
AE reporting	X	X	X	X	X	X	X
Concomitant medication	X	X	X	X	X	X	X

Abbreviations: AE = adverse event; BP = blood pressure; CBC = complete blood count; CHr = reticulocyte hemoglobin content; CRP = C-reactive protein; ECG = electrocardiogram; ET = Early Termination; FACT-An = . Functional Assessment of Cancer Therapy-Anemia; hCG = human chorionic gonadotropin; HR = heart rate; LFT = liver function test; TIBC = total iron binding capacity; TSAT = transferrin saturation; WBC = white blood cell.

^a Subjects are to be dosed for up to 260 weeks (5 years) or 52 weeks if newly enrolled in Amendment 2

^b Follow up Visit is 4 weeks after last dose of study treatment

^c Weekly visits are only for subjects newly initiated to roxadustat until Hb stabilizes

^d Use dry weight in HD subjects

^e To be performed prior to study drug administration. The End-of-Study assessments in the previous roxadustat study may be used for assessments if they were completed within 4 weeks prior to study drug administration.

^f Fasting is preferred, if possible

^g Only collect for subjects who have a baseline special lab collected during prior roxadustat study.

APPENDIX B. DOSING FOR SUBJECTS PREVIOUSLY TREATED WITH PLACEBO

Subjects who received placebo in their previous study will receive roxadustat according to their weight as described in the table below.

If treatment assignment is blinded at the time of enrollment, the subject has been on a stable dosing regimen for at least 2 months and if the last dose is lower than the starting doses described in [Appendix B](#), the subject may continue on the current dosing regimen

Weight-Based Doses for Subjects Previously Treated with Placebo

Low Weight (< 60 kg)	Medium Weight (>60 to 90 kg)	Heavy Weight (>90 kg)
70 mg	100 mg	150 mg

APPENDIX C. DOSE ADJUSTMENT GUIDELINES FOR ROXADUSTAT

All dose adjustments should be based on Hb values using a point-of-care device, such as HemoCue® or CritLine®. In the event that the central lab Hb value of the site visit is significantly different and the dose adjustment decision based on the HemoCue® / CritLine® value is being re-considered, the Medical Monitor should be contacted, if possible.

Dose adjustment reviews will occur on Week 4, and at intervals of every 4 weeks thereafter (Weeks 8, 12, 16, etc.), except in the event of excessive hematopoiesis, in which case doses may be adjusted at any time. In such cases, dose adjustment reviews are resumed at 4-week intervals. For example, if the subject's Hb increases > 2.0 g/dL from Week 1 to Week 3, the subject's dose is reduced by one dose step at Week 3. The next dose adjustment review should occur 4 weeks later at Week 7. If the dose adjustment interval falls on a non-study visit week (starting Week 4), the dose adjustment review should be performed at the next scheduled study visit if a dose adjustment was not required at the previous visit. For example, if a subject's visit is scheduled for Weeks 6 and 8, and the dose adjustment would occur at Week 7, then the dose adjustment should be evaluated at the Week 8 visit.

All subjects will be dosed orally TIW during the Treatment period. During the course of the study, the dose and the dosing frequency may be changed to optimize efficacy and tolerability based on the clinical judgment of the investigator and study medical monitor. If a subject requires < 20 mg TIW (ie, < 60 mg per week) to maintain the target Hb level, the dosing frequency should be reduced in a step-wise fashion eg, TIW to BIW, BIW to QW, QW to Q-2 Week etc. The Medical Monitor should be notified as soon as possible of such dose change. The maximum roxadustat dose is 3.0 mg/kg per dose or 400 mg (whichever is lower).

The following scenarios are defined as “excessive hematopoiesis”;

Hb increases by > 2.0 g/dL at any time within a 4 week period: reduce the dose by one dose step.

Hb reaches or exceeds 13 g/dL: hold dosing, check Hb weekly. Resume dosing when Hb < 12.0 g/dL (for US subjects central lab Hb value preferred), at a dose that is reduced by two dose steps.

For subjects on prolonged dose-hold, with stable (not dropping) Hb, PI may use discretion to schedule less frequent visits. Anytime Hb is assessed via HemoCue®/CritLine®/local lab, a central lab Hb should be obtained as well.

Given the complexity in roxadustat dose adjustments, and the need to take into account the various clinical parameters in roxadustat dose titration, one would not consider it a protocol deviation when study subjects are dosed based on their clinical circumstances, whether or not it is concordant with the roxadustat dose adjustment guidelines unless it was related to “excessive hematopoiesis” (eg, Hb ≥ 13 g/dL, requiring a dose hold) or “Overdose” (prescribed > 3.0 mg/kg per dose or 400 mg per dose whichever is lower)

Roxadustat Dose Adjustment Rules				
Change in Hb from 4 weeks earlier (g/dL)	Hb < 10.5 g/dL	Hb 10.5 to 11.9 g/dL	Hb 12.0 to 12.9 g/dL	Hb ≥ 13.0 g/dL
< -1.0	↑	↑	No change	Hold, then resume dosing when: Hb < 12 g/dL, at a dose that is reduced by two dose steps Subjects are to return weekly to monitor Hb until dosing can be resumed**
-1.0 to 1.0	↑	No change	↓	
> 1.0	No change	↓	↓	

Dose Adjustment for Excessive Hematopoiesis: At any time during the Treatment Period if Hb increases by >2.0 g/dL within 4 weeks, the dose should be reduced by one dose step. ** For subjects on prolonged dose-hold, with stable (not dropping) Hb, PI may use discretion to schedule less frequent visits. Anytime Hb is assessed via HemoCue®/CritLine®/local labs, a central lab Hb should be obtained as well
 
Dose Increases and Reductions: Dose increases (↑) and reductions (↓) are preset to dose steps. The dose steps are as follows: 20, 40, 50, 70, 100, 150, 200, 250, 300, and 400 mg. Example: A dose increase at a dose of 70 mg results in 100 mg as the new dose. A dose reduction at a dose of 150 mg results in 100 mg as the new dose. Note: Maximum dose capped at 3.0 mg/kg per dose or 400 mg, whichever is lower.
 
*Transition from Correction to Maintenance Phase will occur once the central laboratory Hb value is ≥ 11 g/dL and ≥ 1 g/dL from baseline

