	
Rescue Medication:
 
If a subject is not responding adequately to roxadustat, and rescue therapy is considered a medical necessity by the investigator, rescue therapy will be allowed for a subject provided this has been discussed with the study medical monitor, or is deemed to be an immediate medical necessity by the investigator.
 
The three options for rescue therapy are as follows:
 
Blood Transfusion: For subjects requiring a blood transfusion, administration of study medication may continue.
 
Iron Supplementation: Oral iron should be the first-line option for iron supplementation. Intravenous (IV) iron supplementation may be considered if the following criteria are met:
 
The subject has not responded adequately to 2 or more dose increases or reached the maximum dose limit and Ferritin saturation is <50 ng/ml or transferrin saturation (TSAT) is <10%
 
OR
 
The subject is intolerant of oral iron therapy and Ferritin saturation is <50 ng/ml or TSAT is <10%
 
roxadustat treatment should continue during IV and oral iron supplementation. The investigator may discontinue IV iron supplementation once he no longer considers the subject to be iron deficient. The investigator should carefully monitor the subject's Hb response after IV iron supplementation.
 
Erythropoiesis-stimulating agents (ESAs): ESAs are not to be concurrently administered with roxadustat . Once a subject is considered a treatment failure due to a lack of efficacy and/or lack of tolerability of roxadustat , and ESA treatment is initiated per the treating physician, roxadustat must be permanently discontinued and the subject is to be discontinued from the study. In the event of an extenuating circumstance during which a subject inadvertently receives an ESA for a short period of time (e.g., recent bleeding, disruption of roxadustat dosing due to hospitalization or vacation, etc.) the study medical monitor should be contacted to evaluate the appropriateness of continuing treatment with roxadustat.
 
Dose Adjustments for Roxadustat
 
Dose adjustments will occur according to Appendix C. All subjects in the roxadustat arm will be dosed orally TIW during the Treatment Period. During the course of the study, the dose and the dosing frequency may be changed to optimize efficacy and tolerability based on the clinical judgment of the investigator and study medical monitor. The maximum roxadustat dose is 3.0 mg/kg per dose or 400 mg, whichever is lower.
 
All dose adjustments as well as assessments of excessive hematopoiesis are based on Hb values using a point-of-care device such as HemoCue® or CritLine®. In the event that the central lab Hb value of the site visit is significantly different and the dose adjustment decision based on the HemoCue® or CritLine® value is being reconsidered, the Medical Monitor should be contacted, if possible. The determination of Hb response is based on the central laboratory Hb value.
 
Dose adjustment reviews will occur on Week 4, and at intervals of every 4 weeks thereafter (Weeks 8, 12, 16, etc.) except in the event of excessive hematopoiesis, in which case doses may be adjusted at any

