Study Procedures:	See Schedule of Study Assessments (Appendix A)
Investigational Product, Dose, and Mode of Administration:	Subjects will receive 20, 50, and 100 mg of roxadustat as an oral solid dosage (OSD). All OSDs must be administered whole. Initial Doses Subjects who received roxadustat in a previous study will continue to receive roxadustat at the same dose and dosing frequency (three times weekly [TIW], twice weekly [BIW], or once weekly [QW] as they received at the end of their last study, unless a dose adjustment is required. Subjects who received placebo in their previous study will start treatment with roxadustat according to their weight as described in Appendix B . If treatment assignment is blinded at the time of enrollment, the subject has been on a stable dosing regimen for at least 2 months prior to the switch and if the last dose is lower than the starting doses described in Appendix B , the subject may continue on the current dosing regimen. Dose Adjustment Rules Guidelines for dose adjustments are provided in Appendix A .
Efficacy Endpoints and Assessments:	Mean monthly Hb values over time Number (%) of subjects maintaining monthly (defined as a 4-week interval) mean Hb at ≥ 10 g/dL during study participation upon correction (defined as having achieved two consecutive Hb values of ≥ 10 g/dL) Number (%) of subjects maintaining Hb between 10-13 g/dL for at least 60% of scheduled Hb assessments after the first Hb value is 10 g/dL or higher Composite rate of summarized rescue therapy events (transfusions, IV iron, ESAs) and rate of individual rescue therapy events Number (%) of subjects with phlebotomies Roxadustat weekly total doses over time Dose adjustment frequencies Hb variability Number (%) of subjects withdrawn from the study due to inadequate efficacy
Safety Assessments:	Vital signs, clinical laboratory values, and changes in physical examinations AEs and serious adverse events (SAEs)

Exploratory Laboratory Evaluations:	Collect the following labs only if a baseline value is available for the subject (i.e., test was done prior to start of study drug treatment in previous roxadustat study): Reticulocyte hemoglobin content (CHr); High sensitivity C-reactive protein (hs-CRP); Hepcidin levels in serum; Additional biomarkers.

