1.6.2. Efficacy

Data from a 4-week dose ranging study in anemic subjects with CKD not on dialysis (Study FGCL-SM4592-017) suggest that roxadustat promotes erythropoiesis at lower doses in subjects

with CKD than in healthy subjects. With 0.7 mg/kg TIW dosing, mean Hb increased by 1.0 g/dL over a 6-week period in anemic subjects with CKD who completed 4 weeks of dosing; greater mean Hb increases of 2.0 to 2.3 g/dL occurred at roxadustat doses of 1.5 and 2.0 mg/kg TIW, respectively. Hemoglobin responder (Hb increase of ≥ 1.0 g/dL) rates were 62%, 60%, 91%, and 100% in the roxadustat cohorts receiving 0.7, 1.0, 1.5, and 2.0 mg/kg TIW, respectively. The Hb responses were also greater at the higher roxadustat doses (1.5 to 2.0 mg/kg) in the BIW dosing groups. With the additional criterion that Hb achieve a level of ≥ 11 g/dL as well as increasing by ≥ 1.0 g/dL, the Hb responder rate at 2.0 mg/kg of roxadustat IW and TIW was 89% and 91%, respectively. The rapid rates of rise in Hb with roxadustat treatment were not accompanied by elevations in blood pressure (BP), as has been reported with ESA treatment (Eschbach et al. 992-1000).

Data from a 16 to 24-week treatment Phase 2b study in subjects with CKD not on dialysis (Study FGCL-4592-041) showed that absolute and weight-based doses of roxadustat, administered TIW and BIW, effectively corrected and maintained Hb levels to a Hb target of 11 g/dL (range of 11-13 g/dL in 96 subjects and 10.5-12.0 g/dL in 48 subjects).

Data from 48 HD and 12 PD subjects enrolled in a 12-week incident-dialysis study (Study FGCL-4592-053), using similar tiered, weight-based initial doses as study FGCL 4592-041, indicate increases in mean Hb of approximately 2 g/dL after six weeks of treatment. Subjects were randomized to receive no iron, oral iron or IV iron. The Hb responses were indistinguishable between the oral and IV iron arms; subjects in the no iron arm had a similar Hb response during the first 8 weeks of treatment which plateaued during the last 4 weeks of treatment, suggesting that with long-term roxadustat treatment, iron supplementation may be necessary. However, data suggest that supplementation with oral iron is as effective as IV iron, and is recommended as the first-line option for iron supplementation in the Phase 3 studies. Starting roxadustat doses between 1.0 and 1.6 mg/kg appeared adequate to correct Hb in these subjects.

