4.3. Study Treatment

4.3.1. Dose and Schedule

Subjects who received roxadustat in a previous study will continue to receive roxadustat at the same dose and dosing frequency (TIW, BIW, or QW) as they received at the end of their last study, unless a dose adjustment is required.

Subjects who received placebo in their previous study will receive roxadustat by weight category as described in [Appendix B](#).

If treatment assignment is blinded at the time of enrollment, the subject has been on a stable dosing regimen for at least 2 months and if the last dose is lower than the starting doses described in [Appendix B](#), the subject may continue on the current dosing regimen.

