4.3.2. Dose Adjustments

Guidelines for dose adjustments are provided in C. In general:

- The Hb thresholds for dose adjustments are < 10 g/dL for dose increases and \geq 12 g/dL for dose reductions
- Dose adjustment rules are based on changes in Hb values over 4 weeks and whether the Hb target has been reached or exceeded.
- Dose increases and decreases are pre-set at the dose steps described in [Appendix A](#).
- The maximum dose is 3.0 mg/kg.
- The time interval between dose adjustment reviews should be 4 weeks, except in the event of excessive hematopoiesis (when the subject's dose should be reduced), or rapidly declining Hb (when the subject's dose should be increased). For example, even if a subject's dose is not increased or decreased following a dose adjustment review visit, the next dose adjustment review will be 4 weeks after the last dose adjustment review.
- For subjects who received placebo in their previous study, no dose adjustment will occur from Weeks 1 through 4 except in the event of excessive hematopoiesis or rapidly declining Hb.
- For subjects who received roxadustat, or blinded study drug, and on a stable dose for the past 2 months, in a previous study, dose adjustment review will occur 4 weeks from the last dose adjustment review in the previous study.
- During the course of the study, the dose and the dosing frequency may be changed to optimize efficacy and tolerability based on the clinical judgment of the investigator and study medical monitor.

In the event of an extenuating clinical circumstance (e.g., recent bleeding, disruption of dosing due to hospitalization or vacation, etc.), the investigator may dose a subject outside of the dose adjustment parameters provided this has been discussed with the study medical monitor.

Dose Frequency Adjustments should be done according to [Appendix C](#).

Dose Adjustment for Excessive Hematopoiesis

At any time during the treatment period, if Hb increases by > 2.0 g/dL in 2 weeks that is not due to an RBC transfusion the dose should be reduced by one dose step ([Appendix A](#)).

If there are clinical concerns for a subject's excessively high Hb value outside the dose adjustment intervals (as described in [Appendix A](#)), the investigator may adjust the dose immediately; the investigator may also decide to perform a therapeutic phlebotomy in addition to the dose adjustments—these situations should be documented and discussed with the study medical monitor whenever possible.

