3 STUDY DESIGN

This is an open-label, long-term maintenance study of roxadustat anemia therapy in dialysis and non-dialysis subjects with CKD who completed the treatment period of a Phase 2 roxadustat anemia study in the U.S.

Subjects who received roxadustat in a previous study continued to receive roxadustat at the same dose and frequency as they received at the end of the treatment period in their previous study, unless a dose adjustment was required, at time of switching over to this study. Roxadustat was supplied in an open-label manner to all subjects.

This study (amendment 2) accommodated the potential for prior study participants on a placebo, to switch to this study: Subjects who received placebo in their previous study could start treatment with roxadustat at starting doses according to their weight (Appendix B of the protocol). Planned total study duration was up to 312 weeks (6 years), including up to an additional 1 year under Amendment 2.

Study visits were scheduled every 2 weeks, for the first 104 weeks (2 years) of study drug treatment (time on the previous Phase 2 studies of roxadustat), followed by every 4 weeks until the end of the treatment period.

After the end of treatment (defined as the last day a subject receives study drug) the subjects returned for a follow-up visit 4 weeks later.

The baseline Hb value for efficacy analysis is defined as the mean of the central laboratory Hb value from the baseline visit at Day 1 (prior to receiving the first dose of study drug in this study), plus any other central lab Hb values within 15 days prior to Day 1.

Safety is assessed by vital signs, physical examinations, clinical laboratory values (serum chemistries including liver function tests [LFTs] and complete blood counts [CBC]), electrocardiograms (ECGs), AEs and concomitant medication reporting. Clinical laboratory tests, including LFTs and Hb levels, could y be assessed at additional times on unscheduled visits for safety reasons.

Fifteen subjects entered this study: 1 subject from FGCL-4592-040 and 14 subjects from FGCL-4592-041. All subjects received Roxadustat prior to entering this study (0 subject received placebo). Descriptive analyses will be performed for all subjects.

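### The protocol gives two incompatible dosing-frequency rules for subjects already on roxadustat, and the SAP does not say whether a frequency change counts as a dose adjustment

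*Protocol*

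**What the plan says.** Two groups of statements cover dosing frequency for subjects who arrive already on roxadustat.

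**TIW for everyone.** Appendix C: "All subjects will be dosed orally TIW during the Treatment period". The synopsis, under dose adjustments: "All subjects in the roxadustat arm will be dosed orally TIW during the Treatment Period".

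**Previous frequency kept.** Section 4.3.1 makes an exception where an adjustment is needed, and otherwise continues these subjects "at the same dose and dosing frequency (TIW, BIW, or QW) as they received at the end of their last study". The synopsis, under initial doses, has them continue "at the same dose and dosing frequency (three times weekly [TIW], twice weekly [BIW], or once weekly [QW] as they received" when the parent study finished. Section 4.1 gives the same rule without listing frequencies. The synopsis therefore stands on both sides.

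Section 4.3.2 adds "Dose Frequency Adjustments should be done according to" Appendix C. Appendix C lets dose and frequency be changed later on clinical judgment. It also calls for stepwise frequency reduction when a subject needs less than 20 mg TIW. Its dose steps and its cap are both expressed per dose.

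On the analysis side, SAP Section 3 lists "1 subject from FGCL-4592-040 and 14 subjects from FGCL-4592-041", all previously on roxadustat, and reports that they continued at the same dose and frequency unless an adjustment was required. Protocol Section 1.6.2 describes study 041 as using "absolute and weight-based doses of roxadustat, administered TIW and BIW". SAP Sections 4.1 and 8.1 summarize average weekly dose by period and count subjects with an increase, a decrease or a hold. They do not mention frequency changes.

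**The concern.** A subject who finished the parent study on BIW has two different regimens under this protocol, depending on which page the site reads. The provisions in Appendix C for later frequency changes and for step-down below 20 mg TIW do not settle the frequency at entry, because neither exempts a subject who arrives on BIW or QW. No passage says what happens to mg per dose if the frequency is changed.

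Two things are at stake. The first is weekly exposure in subjects already established on treatment. The second is the secondary objective, which concerns doses and dose adjustments. The SAP's counts depend on what qualifies as an increase or a decrease, and that is undefined for a change in frequency. This second gap remains whichever frequency rule the sponsor intends, because Appendix C itself calls for frequency reductions.

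**Working it through.** **Inputs.** Doses per week: TIW 3, BIW 2, QW 1. Appendix C dose steps: 20, 40, 50, 70, 100, 150, 200, 250, 300 and 400 mg. Appendix C cap: 3.0 mg/kg or 400 mg per dose, whichever is lower. Subjects entered: 15 (SAP Section 3).

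**The plan's own figure.** Weekly dose = mg per dose × doses per week. Appendix C equates 20 mg TIW with 60 mg per week: 20 × 3 = 60, reproduced exactly.

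**Entry on frequency f, moved to TIW at unchanged mg per dose.** Relative change = 3/f − 1.

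| Prior frequency | Change in weekly dose | Example at 100 mg per dose |
|---|---|---|
| BIW (f = 2) | 3/2 − 1 = +50% | 200 to 300 mg/week |
| QW (f = 1) | 3/1 − 1 = +200% | 100 to 300 mg/week |

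If the previous regimen is kept, the change is 0%. It is also 0% if mg per dose is cut to 2/3 (BIW) or 1/3 (QW). The range over what a site might do is therefore 0% to +50% for BIW and 0% to +200% for QW.

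**Comparison with single upward steps.** 20→40 +100%; 40→50 +25%; 50→70 +40%; 70→100 +42.9%; 100→150 +50%; 150→200 +33.3%; 200→250 +25%; 250→300 +20%; 300→400 +33.3%. A 50% rise equals or exceeds eight of the nine steps. It crosses none of them, because mg per dose does not move. The cap does not limit it for the same reason.

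**The counting gap, using Appendix C's own step-down.** Assume a subject at 20 mg, the lowest step, whose frequency is reduced with mg per dose held:

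- TIW to BIW: 60 to 40 mg/week, 2/3 − 1 = −33.3%.
- BIW to QW: 40 to 20 mg/week, 1/2 − 1 = −50%.

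A count based on mg per dose records no decrease in either case. The opposite error is also possible. Moving from 150 mg BIW (300 mg/week) to 100 mg TIW (300 mg/week) is a lower step per dose with no change in weekly dose. (These are arithmetic illustrations, not suggested regimens.) With 15 subjects, one subject classified differently moves a percentage by 1/15 = 6.7 points.

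**What cannot be computed.** The documents do not give the number of subjects who entered on BIW or QW. It could be zero.

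**The case against.** The strongest reply is that the passages on entry are specific and the TIW sentence is general. Sections 4.1 and 4.3.1 and the synopsis text on initial doses address the entry regimen of roll-over subjects directly. Appendix C is a dose-adjustment guideline, and Section 4.3.2 refers to it for frequency adjustments, not for starting frequency. To produce the 50% rise, a site would have to honour the same dose and disregard the same frequency in one sentence. SAP Section 3, the only account of what happened at entry, says frequency was continued unless an adjustment was required.

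This stands as far as consequences go: it makes the rise conditional and undemonstrated. It does not remove the conflict, because the TIW sentences cover all subjects and no order of precedence is given.

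Several stronger readings are tempting, and the documents do not support them:

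- **All 15 subjects were affected.** Only those entering on BIW or QW could be. Study 041 used TIW and BIW, and nothing shows a QW entrant, so the 200% case rests only on QW being named as an entry option.
- **A false time trend in weekly dose.** SAP 8.1 summarizes dose within this study from week 0. A change on Day 1 sets the level of the first period and alone creates no trend.
- **Neither reading would be reported as a deviation.** The allowance in Appendix C covers departures from the dose-adjustment guidelines made for clinical reasons. It does not mention the entry rule in Section 4.3.1.
- **The change would go unrecorded.** The dosing CRF is not shown, and average weekly dose would reflect the change.

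It is also unknown what wording applied when these subjects entered. The protocol's summary of changes says Amendment 2 altered the dose-adjustment text, and Section 1.6.2 describes subjects already in this study with up to 2 years of data.

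**Conclusion.** The concern holds as an internal inconsistency of moderate severity. Two stated rules give the same roll-over subject different weekly doses. The difference is 50% for BIW and 200% for QW, assuming the TIW sentence is applied and mg per dose is left unchanged. Neither the per-dose cap nor the per-dose steps would catch it. A reader might infer that exposure actually rose at entry; SAP Section 3 reports continuation, so the documents do not show that.

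The analysis gap is separate and does not depend on any of those conditions. As written, the SAP's counts of increases and decreases may miss frequency changes that the protocol itself calls for. Average weekly dose would still show them, and the analysis is descriptive, which limits the damage.

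**What to change.** 1. **Protocol.** Reconcile the TIW sentences in Appendix C and the synopsis dose-adjustment text with Section 4.1, Section 4.3.1 and the synopsis text on initial doses, so that one entry-frequency statement applies to roll-over subjects. State how mg per dose is handled when frequency changes. Which frequency rule applies is for the sponsor to decide.
2. **SAP 8.1, carried into 4.1.** Define that a frequency change is classified as an increase or a decrease by its effect on weekly dose (mg per dose × doses per week).
3. **Data check.** Compare each of the 15 subjects' entry frequency with the dosing records, and report how many entered on TIW, BIW and QW and whether any changed at entry.

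The cost is a few sentences in the protocol and SAP, one programming rule and a check of existing dosing records for 15 subjects. No new procedures are needed. Because these subjects have already entered, items 2 and 3 matter most for the report.

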4.4.3. Rescue Medication

If a subject is not responding adequately to roxadustat, and rescue therapy is considered a medical necessity by the investigator, rescue therapy will be allowed for a subject provided this has been discussed with the study medical monitor, or is deemed to be an immediate medical necessity by the investigator.

The three options for rescue therapy are as follows:

1. Blood transfusion: For subjects undergoing rescue therapy with transfusion, administration of study medication may continue.
2. Iron supplementation: Oral iron should be the first-line option for iron supplementation. IV iron supplementation may be considered if the following criteria are met:

- The subject has not responded adequately to 2 or more dose increases or reached the maximum dose limit and
- Ferritin saturation is <50 ng/ml **or** transferrin saturation (TSAT) is <10%

OR

- The subject is intolerant of oral iron therapy and
- Ferritin saturation is <50 ng/ml **or** TSAT is <10%

Roxadustat treatment should continue during oral and IV iron supplementation. The investigator may discontinue IV iron supplementation once he no longer considers the subject to be iron deficient. The investigator should carefully monitor the subject's Hb response after the IV iron supplementation.

3. ESAs: ESAs are not to be concurrently administered with. Once a subject is considered a treatment failure due to a lack of efficacy and/or lack of tolerability, and ESA treatment is initiated per the treating physician, roxadustat must be permanently discontinued and the subject also is to be discontinued from the study. In the event of an extenuating circumstance during which a subject inadvertently receives an ESA for a short period of time (e.g., recent bleeding, disruption of dosing due to hospitalization or vacation, etc.), the study medical monitor should be contacted to evaluate the appropriateness of continuing treatment with roxadustat.

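### The one-step dose cut for an Hb rise above 2.0 g/dL exempts transfusion in Section 4.3.2 but not in the synopsis or Appendix C, and the time windows differ

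*Protocol*

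**What the plan says.** The protocol states the cut for a fast Hb rise in four places, all in current text.

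- Section 4.3.2, under excessive hematopoiesis, calls for one dose step down "if Hb increases by > 2.0 g/dL in 2 weeks that is not due to an RBC transfusion".
- The Appendix C text says "Hb increases by > 2.0 g/dL at any time within a 4 week period: reduce the dose by one dose step". The synopsis gives the same rule.
- The note in the Appendix C table says "if Hb increases by >2.0 g/dL within 4 weeks, the dose should be reduced by one dose step".

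The last three do not mention transfusion. On which version a site should use, the synopsis says "Dose adjustments will occur according to Appendix C", and Section 4.3.2 also points to that appendix for the guidelines.

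A transfused subject can stay on drug. Section 4.4.3 says "For subjects undergoing rescue therapy with transfusion, administration of study medication may continue".

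Appendix C excuses dosing based on clinical circumstances from being a protocol deviation, whether or not it is "concordant with the roxadustat dose adjustment guidelines unless it was related to" excessive hematopoiesis or overdose.

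**The concern.** Red-cell transfusion raises Hb whatever the study drug is doing. Section 4.3.2 recognises this and the other three statements do not. For a rise above 2.0 g/dL produced by transfusion, one part of the protocol orders a cut and another exempts it. Section 4.4.3 frames rescue as a response to inadequate effect, so a cut would usually go in the wrong direction. If the transfusion followed a bleed, the cut would still respond to something the drug did not cause.

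The windows differ for subjects without a transfusion as well. A rise that passes 2.0 g/dL only over more than 2 and up to 4 weeks triggers the synopsis and Appendix C rule but not the Section 4.3.2 rule.

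Doses and dose adjustments are the secondary objective, and SAP Section 8.1 counts subjects with a dose decrease. It should be clear which rule sites were following.

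**Working it through.** The plan gives no figure to reproduce. The check compares the texts and then works through assumed Hb values.

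**1. The four statements**

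| Place | Window | Rise from transfusion exempt? | Action |
|---|---|---|---|
| Section 4.3.2 | 2 weeks | Yes | One step down |
| Synopsis | 4 weeks | No | One step down |
| Appendix C text | 4 weeks | No | One step down |
| Appendix C table note | 4 weeks | No | One step down |

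**2. Can the same data meet both rules?** Yes. A rise within 2 weeks is also a rise within 4 weeks, and Appendix C's own worked example runs from Week 1 to Week 3, which is 2 weeks. On the 2-weekly visits in Section 4.1 (first 104 weeks of treatment, counting earlier studies), both rules can be tested and they disagree. On 4-weekly visits (the synopsis schedule for subjects coming from roxadustat, and Section 4.1 after week 104), scheduled values cannot test the 2-week rule. The version without the exemption is then the only one in play.

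**3. One case (assumed values).** A subject on 100 mg has Hb 8.0 g/dL four weeks ago and again just before transfusion, then 10.3 two weeks later. The rise is 10.3 − 8.0 = 2.3 g/dL.
- Routine Appendix C table: Hb below 10.5 and change above 1.0 gives no change, so 100 mg.
- Section 4.3.2 rule: exempt, so 100 mg.
- Synopsis and Appendix C rule: one step down the ladder to 70 mg, a cut of (100 − 70)/100 = 30%.

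Elsewhere on the ladder one step is 16.7% (300 to 250 mg) to 33.3% (150 to 100 mg), except 40 to 20 mg, which is 50%.

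**4. When does the missing exemption change the dose?** The inputs are assumed scenarios, not frequencies: pre-transfusion Hb N of 7.0, 7.5, 8.0, 8.5 or 9.0; net rise R of 2.1, 2.5, 3.0 or 3.5; fall before rescue F of 0, 1.0 or 2.0. That makes 5 × 4 × 3 = 60 cells, all with a net rise above 2.0 by construction. Hb now is N + R, and the change from 4 weeks earlier is R − F.

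| F | Routine table: increase / no change / decrease | >2.0 rule fires on R − F | Cut from that rule only |
|---|---|---|---|
| 0 | 0 / 6 / 14 | 20 | 6 |
| 1.0 | 0 / 6 / 14 | 5 | 0 |
| 2.0 | 6 / 8 / 6 | 0 | 0 |
| Total | 6 / 20 / 34 | 25 | 6 |

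With 4-weekly values only, the rule fires in 25 cells. The routine table already cuts in 19 of them, which leaves 25 − 19 = 6 cuts due to the rule alone, all from no change. If a pre-transfusion Hb within the 4 weeks is also available, the rule is tested on R and fires in all 60 cells. Cuts due to the rule alone are then 60 − 34 = 26: 20 from no change and 6 from an increase. An example of the latter is Hb 9.0, then 7.0, then 9.5 after transfusion.

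**5. Does the deviation sentence settle it?** Not clearly. It withholds its latitude for departures related to excessive hematopoiesis, and Appendix C defines that term to include a rise above 2.0 g/dL from any cause. Its only example is Hb of 13 g/dL or more, so a narrower reading is possible.

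**The case against.** The strongest reply is that the protocol already handles this in practice. Section 4.3.2 lets the investigator depart from the dosing rules in extenuating circumstances after discussion with the medical monitor, and recent bleeding is one of its examples. Under Section 4.4.3, "rescue therapy will be allowed for a subject provided this has been discussed with the study medical monitor" or the need is immediate, so the monitor will often know of the transfusion. Appendix C consists of guidelines and itself allows clinical judgment. Read together, Section 4.3.2 could supply the qualifier that the other places lack, since donor cells are not hematopoiesis. This stands to the extent that a wrong cut is avoidable. It does not make the four statements agree, and the synopsis points to the version without the exemption.

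The objection that the grid is invented also stands. It shows where the rules part, not how often. The 26-cell count needs an interim Hb whose availability is unknown.

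Two further inferences are tempting and are not supported. First, 3 of the 6 cells on 4-weekly values end at 9.1, 9.5 and 9.6 g/dL, and Section 4.3.2 says "The Hb thresholds for dose adjustments are < 10 g/dL for dose increases". A reader might conclude that the rule cuts when an increase was due. That threshold is given as a general statement. The operative Appendix C table gives no change in those cells, because Hb had risen by more than 1.0. Second, the routine table also cuts in 34 of 60 cells without regard to transfusion, which might suggest adding an exemption there too. Appendix C already says that departing from that table on clinical grounds is not a deviation.

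Finally, the amendment summary says the dosing algorithm was aligned with the global Phase 3 program. Whether that program exempts transfusion cannot be seen here, so the sponsor should confirm the intended rule.

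**Conclusion.** The point holds as an inconsistency in current text. The same one-step cut carries a transfusion exemption and a 2-week window in Section 4.3.2, and neither in the synopsis or the two Appendix C statements. A transfused subject who stays on roxadustat can be directed to a lower dose for a rise the drug did not cause, unless someone intervenes.

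It is minor. SAP Section 3 reports that 15 subjects entered and describes conduct largely in the past tense. Neither document gives the number of transfusions. The sizes above rest on assumed Hb values.

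A reader might infer that subjects were in fact under-dosed, or that the Hb results are biased. The documents support neither: they do not show how many transfused rises exceeded 2.0 g/dL, which rule sites followed, or how often judgment was used. No effect on the efficacy analysis is claimed.

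**What to change.** 1. In the synopsis, the Appendix C text and the Appendix C table note, add the transfusion exemption that Section 4.3.2 already carries, in the same words.
2. In Section 4.3.2, change the 2-week window to the 4 weeks used in the other three places.
3. In the Appendix C deviation sentence, state that not applying the cut for a rise above 2.0 g/dL, because the rise was due to a red-cell transfusion, is not a protocol deviation.

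Leave the hold at Hb of 13 g/dL or more and the routine table as they are.

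The cost is one phrase in three places, one window and one clause. No new data, visits or analyses are needed.
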